^a Total screening period should not exceed 60 days. If screening is longer than 28 days, BNP should be repeated through the central lab prior to randomization.

^b Study Day 1 is the day of administration of the first dose. **On Study Day 1, all procedures should be performed before study drug administration.**

^c Under the delegation of the Investigator and following Sponsor prior approval for each visit, a patient may be seen by a home health professional, qualified by documented training to perform study-specific procedures. If the visit is completed by home health professional, a limited physical assessment directed to assess for fluid retention and clinical worsening will be performed under the delegation of the Investigator

^d Patients who discontinue from the study prior to the Week 16 study visit will need to be brought back for all early termination assessments (i.e., both an end-of-treatment visit and then a follow-up visit 4 weeks after the date of administration of the last dose of study drug). Patients should complete the end-of-treatment procedures, including the 6MWT, prior to any adjustments being made to their PAH treatment regimen.

^e Screen A eligibility procedures do not need to be repeated on Day 1; however, a review of any changes in eligibility criteria should be evaluated prior to Day 1 procedures, and a urine pregnancy test should be performed for WOCBP.

- ^f Weights taken at home by the patient will begin on Day 2 and should be taken daily for the first 8 weeks and weekly thereafter, preferably at the same time each day and must be recorded in a diary and reviewed with the coordinator during telephone contacts and office visits.
- ^g If clinical worsening is suspected, further clinical evaluations may be required per Section 9.10.32.
- ^h A serum pregnancy test will be performed at Screen A for WOCBP or at any point in time if a pregnancy is suspected. All other pregnancy assessments will be urine pregnancy tests. Additional pregnancy assessments will be performed more frequently if required by local law or requested by local regulatory authorities or IRBs/ECs.
- ⁱ AE assessments on Day 1 should be done following study drug administration.

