6. If a patient is on chronic oxygen therapy, oxygen should be given at their standard rate or as directed by a physician or a protocol.

Reasons for immediately stopping a 6MWT include the following: (1) chest pain, (2) intolerable dyspnea, (3) leg cramps, (4) staggering, (5) diaphoresis, and (6) pale or ashen appearance.

Technicians must be trained to recognize these problems and the appropriate responses. If a test is stopped for any of these reasons, the patient should sit or lie supine as appropriate depending on the severity of the event and the technician's assessment of the severity of the event and the risk of syncope. The following should be obtained based on the judgment of the technician: BP, pulse rate, oxygen saturation, and a physician evaluation. Oxygen should be administered as appropriate.

TECHNICAL ASPECTS OF THE 6MWT**Location**

The 6MWT should be performed indoors, along a long, flat, straight, enclosed corridor with a hard surface that is seldom traveled. The walking course must be 15-30m in length. An approximate 49 to 98-ft hallway is, therefore, required. The length of the corridor should be marked every 3 meters. The turnaround points should be marked with a cone (such as an orange

traffic cone). A starting line, which marks the beginning and end of each lap, should be marked on the floor using brightly colored tape.

Rationale

A shorter corridor requires patients to take more time to reverse directions more often, reducing the 6MWT.

REQUIRED EQUIPMENT

1. Countdown timer (or stopwatch)
2. Mechanical lap counter
3. Two small cones to mark the turnaround points
4. A chair that can be easily moved along the walking course
5. Worksheets on a clipboard
6. A source of oxygen
7. Sphygmomanometer
8. Telephone
9. Automated electronic defibrillator

PATIENT PREPARATION

1. Comfortable clothing should be worn.
2. Appropriate shoes for walking should be worn. A notation should be made in the patient's source documentation of which shoes the patient wore for the first test. Prior to each clinic visit the patient should be called/reminded to ensure they wear this same pair of shoes.
3. Patients should use their usual walking aids during the test (cane, walker, etc.). NOTE – if a patient uses a walking aid for the first test this same aide should be used during all subsequent test whether needed or not.
4. The patient's usual medical regimen should be continued. The patient should continue to take doses of study drug prior to the test.

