##### 3.1.3 Modified Intent-to-treat (mITT) Population

The purpose of this Phase 2 study is to estimate the treatment effect of bardoxolone methyl on 6MWD in patients with PAH, and to identify an appropriate dose for further development. Estimated treatment effect from this study will be used to power future trials of bardoxolone methyl in PAH patients.

The mITT population will include all randomized patients who received at least 28 doses of study treatment, did not undergo heart or lung transplantation during the treatment period, and performed at least one post-baseline 6MWT assessment. The primary population for efficacy analyses of the primary endpoint will be the mITT population. The mITT analysis will be done by randomized treatment, pooling all placebo patients and all active treatment patients.

Since treatment effect is expected to be observed within the first few weeks of treatment and sustained over time, missing data will be imputed using last observation carried forward (LOCF) for mITT analyses. Missing data will only be imputed for the 6MWD analysis.

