### 3.4.4 Efficacy Analysis

Analysis of the 6MWD will be performed using the mITT analysis set on all available data. Missing 6MWD data in Part 1 will be imputed using LOCF as described in Section 3.1.2. No imputation will be performed for missing 6MWD data in Part 2.

The CRF nominal study visits (i.e., Week 4, Week 8, Week 12, and Week 16) will be used for all 6MWT efficacy analyses. For subjects that prematurely discontinue treatment before Week 16 with a 6MWT recorded at the End of Treatment (EOT) assessment, that EOT 6MWD will be used in analysis for the nominal protocol visit most closely matching the subject's visit schedule. For all other efficacy analyses, the value closest to the target study day should be used (Section 3.7.2). In Part 1, LOCF will be applied to impute missing 6MWD values after analysis values are obtained taking into consideration the End of Treatment assessment, if applicable. For all other efficacy variables besides 6MWD, LOCF should not be used, and no imputation for missing data should be performed.

Analysis will pool all active doses within cohort for comparison with placebo in Part 1.

The analyses will be repeated for subgroups defined by PAH etiology in Part 1 (i.e., connective tissue disease vs non-connective tissue disease).

Given the exploratory nature of this study, sensitivity analysis may be performed in an ad hoc manner.

Plots will be generated to summarize 6MWT results by randomized treatment, pooling all placebo patients and all active patients into various subgroups:

- All PAH patients (Cohorts 1, 2, 3a, and 3b patients)
- All CTD-PAH patients (CTD-PAH patients in Cohorts 1, 2, and 3a)
- All Non-CTD PAH patients (Non-CTD PAH patients in Cohorts 1, 2, and 3b)
- All PH patients (Cohorts 4a, 4b, 4c, 4d)

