### 3.4.4.1 Primary Efficacy Endpoint

The primary measure of efficacy is the overall treatment effect across Week 4, Week 8, Week 12, and Week 16 for change from baseline in exercise capacity, as measured by the 6MWD, for bardoxolone methyl compared to placebo. The difference in mean overall change from baseline through Week 16 (active – placebo) will be used to assess the effect of bardoxolone methyl on 6MWD in patients with PAH. A lower 6MWD reflects greater PAH severity thus, a positive change from baseline suggests an improvement.

As supportive analysis to the primary endpoint, the mean change from baseline and treatment differences will be estimated for each visit. The actual values and changes from baseline in 6MWD will be summarized using descriptive statistics at each scheduled visit. Walk distances collected at any duration other than 6 minutes will not be included in the analysis of 6MWD unless the reason for not walking 6 minutes is one listed in the ATS guidelines as a reason for stopping the test immediately (i.e., chest pain, intolerable dyspnea, leg cramps, staggering, diaphoresis, and pale or ashen appearance).

Baseline for 6MWD will be the average of scheduled predose assessments (e.g., Screen A and Day 1) collected prior to the first administration of study drug. Similarly, two 6MWD measurements collected at Week 4 and again at Week 16. Multiple measures are within the Week 4 and Week 16 visits, and the 6MWD value used as at these visits is the calculated average within these visits.

The mean overall treatment effect across all visits for change from baseline in 6MWD will be estimated and compared with placebo through 16 weeks of treatment by mixed-model repeated measures (MMRM), with treatment group, visit, and the interaction between treatment and visit as fixed factors. Visits at Weeks 4, 8, 12, and 16 will be used. A compound symmetry covariance matrix will be assumed. Point estimates and 95% confidence intervals for the mean change from baseline for each treatment as well as the treatment difference (active-placebo) will be provided overall and at each protocol scheduled timepoint.

Separate mixed models will be used to compare (1) pooled bardoxolone methyl doses with placebo and (2) individual dose levels with placebo. The first model contains two treatment groups with data at four timepoints. Example SAS code to obtain estimated treatment differences is provided below.

```
Proc Mixed data=x order=data;

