## 3.7 Missing and Partial Data

For the analysis of safety variables, partial dates may be imputed; otherwise, missing data will be treated simply as missing. However, if an AE onset date is missing, it will be imputed (see Appendix C). The algorithms for imputation of partial dates depend upon the parameter (see Appendix C). The central laboratory uses assays that have lower limits of detection (LLD). Continuous laboratory data results which are less than the lower limit of detection or above the upper limit of quantification will be imputed to the value of the lower or upper limit plus or minus one significant digit, respectively (e.g., if the result of a continuous laboratory test is  $< 20$ , a value of 19 will be assigned).

Imputation for missing efficacy data (i.e., 6MWD) is described with the efficacy analysis Section 3.4.4.

### 3.7.2 Analysis Windows for Part 1

For all Part 1 analyses of 6MWD, scheduled visits will be used regardless of study day, as well as any unscheduled or end of treatment visits within the visit windows listed in Section 3.7.4. If an unscheduled or EOT visit falls within the same window as a nominal study visit, the average of the two will be used. For subjects that prematurely discontinue treatment before Week 16 with a 6MWT recorded at the End of Treatment (EOT) assessment, that EOT 6MWD will be used in analysis for the nominal protocol visit most closely matching the subject's visit schedule.

For all other Part 1 efficacy and safety analyses, if multiple assessments fall within the same analysis visit, the assessment closest to the target study day specified in the protocol will be used. If two assessments are equidistant from a post-baseline target visit day, the earlier assessment will be used. Visits that do not occur in all versions of the protocol (i.e., Week 6) should be treated as unscheduled assessments.

### 3.7.3 Analysis Windows for Part 2

Part 2 assessments will be used in efficacy and safety analyses if the assessment was collected within the scheduled window below. Study day will be calculated for each assessment and compared to the protocol defined study day for each visit. In general, analysis in Part 2 will be defined as follows:

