**Table 2. Visit Windows for Unscheduled and End of Treatment Visits in Part 1**

Analysis Visit	Study Day	Analysis Window
Day 1	1	$\text{Study Day} \leq 1$
Week 1	7	$2 \leq \text{Study Day} \leq 10$
Week 2	14	$11 \leq \text{Study Day} \leq 20$
Week 4	28	$21 \leq \text{Study Day} \leq 42$
Week 8	56	$43 \leq \text{Study Day} \leq 70$
Week 12	84	$71 \leq \text{Study Day} \leq 98$
Week 16	112	$99 \leq \text{Study Day} \leq 119$

Records from unscheduled or end of treatment visits that do not fall within an analysis window will be listed, but will not be analyzed. Per Section 3.4.4, for the 6MWT analysis, if use of the visit windows yields more than one value for a particular visit, the average of the two or more values will be used for analysis. For all other analyses, including the eGFR and safety analyses, the value closest to the target study day should be used (Table 2).

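### Walks ended early for a symptom outside six listed reasons lose their recorded distance; separately, an end-of-treatment walk can be averaged with a completed visit before LOCF carries it forward

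*SAP*

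**What the plan says.** **Walks ended early.** SAP 3.4.4.1: "Walk distances collected at any duration other than 6 minutes will not be included in the analysis of 6MWD unless the reason" for the short walk "is one listed in the ATS guidelines as a reason for stopping the test immediately (i.e., chest pain, intolerable dyspnea, leg cramps"; the list ends with staggering, diaphoresis and a pale or ashen appearance. Protocol Appendix 1 (Safety Issues) introduces the same six with "Reasons for immediately stopping a 6MWT include the following". Later in that appendix, when a patient will not or should not continue, the tester ends the walk and records the distance, the stopping time and the reason. A patient who only pauses keeps the timer running and still completes a six-minute test.

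**EOT walks.** Early discontinuers are called back for an EOT walk (Protocol 7.5, Table 4, footnote d): "Patients should complete the end-of-treatment procedures, including the 6MWT, prior to any adjustments being made to their PAH treatment regimen". SAP 3.4.4 and 3.7.2 assign that walk to the nominal visit that best fits the patient's schedule. SAP 3.7.2 also states: "If an unscheduled or EOT visit falls within the same window as a nominal study visit, the average of the two will be used". SAP 3.7.4, below Table 2, repeats that where a visit has more than one walk "the average of the two or more values will be used for analysis". On the order of steps, SAP 3.4.4 says "LOCF will be applied to impute missing 6MWD values after analysis values are obtained taking into consideration the End of Treatment assessment, if applicable". The reason given for LOCF, in SAP 3.1.3, begins "Since treatment effect is expected to be observed within the first few weeks of treatment and sustained over time".

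**The concern.** The protocol's six reasons tell a technician when to halt a test for safety. The SAP closes that list (*i.e.* in place of *include*) and uses it to decide which distances count as efficacy data. A patient who has to end a walk for an unlisted symptom has a poor result on the worksheet. The analysis discards it and may substitute a value from an earlier visit.

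The averaging rule has a milder effect of the same kind. A walk taken at discontinuation, up to 14 days after a completed visit, is treated as a replicate of that visit, and the blend then stands for every later missing visit. Whether this happens depends only on the calendar day of the EOT walk.

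SAP 3.1.3 says the estimated 6MWD effect will be used to power later trials. If late worsening or symptom-ended walks are more frequent on active treatment, these rules overstate benefit; if more frequent on placebo, they understate it; if balanced, they cancel in the arm difference.

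**Working it through.** **1. Symptoms the six reasons miss.** Protocol 11.7 names nine events as common in this population. Shortness of breath, exertional dyspnea and chest pain correspond to listed reasons. Light-headedness/dizziness, syncope, palpitations, fatigue and hypoxemia do not. The ninth, edema/fluid retention, is not an obvious reason to end a walk.

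**2. What replaces a dropped walk** (Protocol Tables 3 and 4).
- Week 16 in all cohorts, and Week 4 in Cohorts 1 and 2: two walks are scheduled, so the other can supply the visit.
- Weeks 8 and 12: one walk, so LOCF fills the visit from an earlier analysis value.
- Week 4 in Cohorts 3 and 4: one walk and no earlier post-baseline value; the SAP does not say whether baseline is carried.

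**3. Scale of the first effect.** With an equal shortfall in both arms, bias at a visit = (share lost, active − share lost, placebo) × shortfall. Neither term is in the documents. For illustration only, take a 60 m/min walker stopping at minute 5 (60 × 1 = 60 m short) to minute 3 (60 × 3 = 180 m short), and an arm difference of 1 to 5 percentage points. This gives 0.01 × 60 = 0.6 m to 0.05 × 180 = 9 m at that visit, and a quarter of that (0.15 to 2.25 m) in the four-visit mean if one visit is affected.

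**4. When EOT averaging applies.** Table 2 windows: Week 4, Days 21–42; Week 8, 43–70; Week 12, 71–98; Week 16, 99–119. The mITT set needs at least 28 doses. With visits on target days, the possible EOT days are 29–111 without 56 and 84: 83 − 2 = 81. Days 29–42, 57–70 and 85–98 fall in the window of the visit just completed: 3 × 14 = 42 days. On the other 39 days the EOT walk stands alone at the next visit and is carried undiluted. Reading the closest-visit sentence as nearest target day selects the same visit on every day, apart from ties on Days 42, 70 and 98, which Table 2 gives to the earlier visit.

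**5. Effect per patient.** Let D be the change since the completed visit, with two values in the window. Entries are fractions of D at Weeks 4/8/12/16.

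| EOT day | SAP rule | EOT walk carried | Lost, four-visit mean | Lost, Week 16 |
|---|---|---|---|---|
| 29–42 | 0.5/0.5/0.5/0.5 | 0/1/1/1 | (3 − 2)/4 = 0.25D | 0.5D |
| 57–70 | 0/0.5/0.5/0.5 | 0/0/1/1 | (2 − 1.5)/4 = 0.125D | 0.5D |
| 85–98 | 0/0/0.5/0.5 | 0/0/0/1 | 0 | 0.5D |

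With EOT days spread evenly: 14 × (0.25 + 0.125 + 0)/81 = 0.065D overall and 42 × 0.5/81 = 0.26D at Week 16.

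Example (assumed): baseline 350 m, Week 4 360 m, Week 8 on Day 56 365 m, EOT on Day 68 305 m. The SAP carries (365 + 305)/2 = 335 m: Week 16 change −15 m, four-visit mean −8.75 m. Keeping Week 8 and carrying the EOT walk gives −45 m and −16.25 m.

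With two Week 4 walks (Cohorts 1 and 2), the carried value keeps one half of D (average of averages) or one third (average of three walks); the SAP does not say which.

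**6. Effect on the arm difference.** Once LOCF has filled all four visits, and without the optional BMI covariate, the compound-symmetry model's overall contrast equals the difference of simple means. The shift is therefore (difference in worsening rate) × D × 0.065 or 0.26. Rates and drops are assumed; results use the unrounded factors.

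| Worsening, one arm vs other | D | Overall | Week 16 |
|---|---|---|---|
| 8% vs 5% | 60 m | 0.12 m | 0.47 m |
| 12% vs 5% | 80 m | 0.36 m | 1.45 m |
| 15% vs 5% | 100 m | 0.65 m | 2.59 m |

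In the middle row, EOT timing alone moves the pair from 0/0 (no EOT day in an averaging window) to 1.4/2.8 m (all on Days 29–42). With assumed between- and within-patient SDs of 40 and 25 m, the standard errors overall/Week 16 are 18.1/20.4 m at 16:8 patients and 10.5/11.8 m at 48:24.

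**7. When carrying the EOT walk is nearer the truth.** Let a fraction f of the drop persist. At Week 16, |1 − f| < |0.5 − f| requires f > 0.75. For the four-visit sum, 3 beats 2 as an estimate of 3f when f > 0.833 (last visit Week 4), and 2 beats 1.5 as an estimate of 2f when f > 0.875 (Week 8); after Week 12 there is no difference. For a lasting drop with walk error SD 25 m, the average has the lower mean squared error when D²/4 + 625/2 < 625, that is, D below about 35 m.

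**The case against.** On short walks: patients may rest with the timer running, second walks exist at some visits, and Protocol 11.7 is a list of adverse events exempt from individual expedited reports, not of reasons for ending walks. All of this narrows the reach of the rule. It does not change what happens when a walk at Week 8 or 12 is ended for dizziness.

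On averaging: it is a consistent choice. Baseline and repeat walks are averaged too, and SAP 1.10 describes 6MWD as highly variable. A sustained treatment effect supports averaging two walks as much as carrying the last one. The comparison in steps 5 and 6 sets one convention against another, under a lasting drop measured without error. These objections largely stand, and they are why averaging is the secondary point. The closest-visit sentence could also be read as letting the EOT walk supply that visit's value alone. But SAP 3.7.2 puts it beside an averaging sentence that names EOT visits, so the two at least need reconciling.

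A reader might infer that these rules favour the drug. The documents give no arm-specific rates, so neither direction is supported. A reader might also infer that no planned sensitivity analysis covers the point. The readable text offers only ad hoc ones, but much of the SAP text after the 6MWD model is redacted, so absence cannot be shown.

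**Conclusion.** The concern holds, at minor severity. The short-walk rule is the firmer part: it discards an outcome that the protocol has recorded and, where no other walk supplies the visit, replaces it with an earlier one. Bias requires the frequency or shortfall of such walks to differ by arm, and its size cannot be estimated from the documents.

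The averaging rule is real but weaker. In the three assumed scenarios it shifts the primary measure by well under 1 m and Week 16 by more, small beside the assumed standard errors. Carrying the last walk is an improvement only for declines that mostly persist and are large relative to walk-to-walk error. A reader might infer that the primary result is materially distorted. The documents do not support that: SAP 1.5.2 rests the dose range on no single endpoint, and Protocol 9.10.32 assesses clinical worsening separately.

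**What to change.** **Short walks (SAP 3.4.4.1).** Include the recorded distance of any walk terminated for a patient symptom. Exclude only walks invalidated by test error or external interruption. The cost is wording and a slightly more variable 6MWD; the data are already collected.

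**EOT walks (SAP 3.4.4, 3.7.2 and the note to Table 2 in 3.7.4).** Keep the completed visit's value at its own visit and let LOCF carry the EOT walk, as the last observation, to later missing visits. Amend both the averaging sentence and the closest-visit sentence, since leaving either unchanged would contradict the new rule. The costs are that single walks are noisier than averages, that a Day 29 walk could stand for Day 56 (27 days early), and that a temporary decline, which Protocol 9.10.32 recognises can occur, would be overstated. No new data are needed.

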### 3.4.5 Safety Analysis

Safety data will be summarized using the safety population. Missing data will not be imputed for safety analyses. With the exception of adverse events, safety results will be summarized by the CRF nominal study visits (i.e., Week 1, Week 2, Week 4, Week 8, Week 12, and Week 16). For subjects that prematurely discontinue treatment before Week 16 with an End of Treatment (EOT) assessment, that EOT will be used in analysis for the nominal protocol visit most closely matching the subject's visit schedule. Similarly, for patients with safety results at an unscheduled visit that unscheduled visit will be used in analysis for the nominal protocol visit most closely matching the subject's visit schedule. For all safety listings except adverse events, if a safety result does not fall within a scheduled visit window, that result will be included in the safety listings but not the safety table summaries.

Moreover, if retest values are available, all safety analyses should use the results closest to the target study day (e.g., Day 28 for Week 4, Day 56 for Week 8, etc.). If two values are equidistant from the target study day, the earliest of those values will be used in all safety analyses.

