#### **3.4.5.2 Laboratory Data**

Laboratory test results include clinical chemistry, hematology, and urinalysis. Continuous lab data, including actual values and changes from baseline, will be summarized using descriptive statistics (including mean, standard deviation, quartiles, median, minima and maxima) for chemistry and hematology parameters. If the scheduled assessment is missing, use the recheck measurement closest in time to scheduled visit (if available).

If a Day 1 laboratory collection occurred after the first dose of study drug, that lab value should not be used as the baseline lab value. The baseline lab value is the last laboratory value collected before study drug administration.

Shift tables will be provided to assess changes from normal to abnormal shifts from baseline to Week 16 for chemistry and hematology parameters.

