### 3.5.5 Safety

Safety analyses described in Section 3.4.4 will be performed on available safety data from Part 2 using the Part 2 treatment groups (BARD, PBO-BARD). Change from baseline summaries of safety described in 3.4.3 will include both change from baseline (Part 1) and change from the end of Part 1 (Week 16) for Part 2.

Analyses of adverse events will count only Part 2 treatment-emergent adverse events (TEAEs), defined as new or worsened events after the Week 16 visit. New or worsened events after Week 16 visit are those events with an AE start date after the Week 16 study visit, or previously recorded AEs with an adverse change in severity (e.g., went from mild to moderate or moderate to serious) after the Week 16 study visit. Similarly, only new onset concomitant medications (date of first dose after the Week 16 visit) will be included in Part 2 summaries.

Shift tables will be provided to assess changes from normal to abnormal shifts from Week 16 to each nominal visit for chemistry and hematology parameters.

Additional details will be provided in the mock Tables, Listings, and Figures.

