### 3.7.4 Analysis Windows for Unscheduled and End of Treatment Visits (Part 1)

Additionally, unscheduled assessments and end of treatment assessments will be used in efficacy and safety analyses if the unscheduled assessment was collected within the scheduled window below. Study day will be calculated for each unscheduled assessment and compared to the protocol defined study day for each visit. In general, analysis windows for unscheduled and end of treatment visits in Part 1 will be defined as follows:

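### In Cohorts 3 and 4, the first scheduled laboratory values after the Week 4 dose increase (Week 6) are left out of the Part 1 by-visit safety summaries when Weeks 4 and 8 are on schedule, and the Part 1 shift tables most likely show Week 16 only

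*SAP*

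**What the plan says.** Protocol 7.1 has Cohorts 3 and 4 increase the dose at Week 4 unless a dose-limiting toxicity is reported, and adds an in-person Week 6 visit for these cohorts. Protocol Table 4 schedules clinical chemistry, BNP and NT-Pro BNP, hematology, urinalysis, vital signs and clinic weight at that visit. Only telephone contacts (Days 31 and 38) fall between Week 4 and Week 6.

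The SAP handles Week 6 as follows.

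- Section 3.4.5 leaves it out of the safety visits: "safety results will be summarized by the CRF nominal study visits (i.e., Week 1, Week 2, Week 4, Week 8, Week 12, and Week 16".
- Section 3.7.2 reclassifies it: "Visits that do not occur in all versions of the protocol (i.e., Week 6) should be treated as unscheduled assessments".
- Section 3.7.4 applies one set of windows to both kinds of analysis: "unscheduled assessments and end of treatment assessments will be used in efficacy and safety analyses". Table 2 gives Week 4 as Days 21–42 and Week 8 as Days 43–70.
- Where a window holds several values: "For all other analyses, including the eGFR and safety analyses, the value closest to the target study day should be used (Table 2". Only the 6-minute walk is averaged.
- Section 3.4.5.2 covers a missing laboratory value: "If the scheduled assessment is missing, use the recheck measurement closest in time to scheduled visit (if available".

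For Part 1 laboratory shifts, section 3.4.5.2 says: "Shift tables will be provided to assess changes from normal to abnormal shifts from baseline to Week 16 for chemistry and hematology parameters". For Part 2, section 3.5.5 plans "changes from normal to abnormal shifts from Week 16 to each nominal visit for chemistry and hematology parameters".

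**The concern.** Safety over 16 weeks against placebo is a secondary objective, and Part 1 is the only placebo-controlled period. Protocol 5.1.3 says transaminases rise after starting treatment or after a dose increase, peak roughly two to four weeks later, and in most patients fall below the upper limit of normal within two weeks of the peak. After initiation, the SAP tabulates Weeks 1, 2 and 4. After the increase, on-schedule data leave nothing before Week 8, four weeks later, although a sample was drawn at two weeks.

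Cohorts 3 and 4 make up most of the trial: 6 × 24 = 144 of about 198 planned patients, and up to 6 × 72 = 432 of 486. At stake is whether the bardoxolone-versus-placebo laboratory tables show the early part of the post-increase response. Dose levels are not compared here; SAP section 3 groups the titration cohorts by randomized treatment only.

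**Working it through.** The plan gives no figure of its own to reproduce. The check uses visit days from Protocol Table 4 and windows from SAP Table 2.

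**1. Can Week 6 be selected?** The allowed days are Week 4 = 25–31, Week 6 = 39–45 and Week 8 = 53–59. The distance is |study day − target day|.

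| Week 6 day | Table 2 visit (target) | Distance, days |
|---|---|---|
| 39 | Week 4 (28) | 11 |
| 40 | Week 4 (28) | 12 |
| 41 | Week 4 (28) | 13 |
| 42 | Week 4 (28) | 14 |
| 43 | Week 8 (56) | 13 |
| 44 | Week 8 (56) | 12 |
| 45 | Week 8 (56) | 11 |

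An on-schedule Week 4 or Week 8 value is at most 3 days from target. The smallest Week 6 distance is 11, and 11 > 3, so Week 6 is chosen in none of the 7 × 7 × 7 = 343 on-schedule day combinations. Filing Week 6 under the nearest target day, as section 3.4.5 could be read, also gives none.

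**2. Missing Week 4 value.** A Week 6 value on Days 39–42 can then be tabulated as Week 4. With the increase on Day 28 it was drawn 39 − 28 = 11 to 42 − 28 = 14 days after the increase, yet it carries a label that normally means before the increase took effect. The documents give no rate for this, and it is an edge case.

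**3. Timing of the expected rise.** Take the increase on Day 28.

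- Peak: Day 28 + 14 = 42 to Day 28 + 28 = 56.
- Mostly below the upper limit of normal by: Day 42 + 14 = 56 to Day 56 + 14 = 70.
- Gap to Week 16: 112 − 70 = 42 to 112 − 56 = 56 days, or six to eight weeks.

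The two-week end of the range coincides with Week 6, the visit left out. The four-week end coincides with Week 8, which is kept. A Week 16 shift table falls after both.

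**4. Comparison with Part 2.** Cohorts 3 and 4 may titrate up at Week 20 (Day 140). SAP Table 1 gives Week 22 (Day 154) its own window, Days 148–161. The lag is 154 − 140 = 14 days, the same as 42 − 28 = 14 in Part 1. Part 2 shift tables run to each nominal visit. So the uncontrolled extension tabulates the two-week post-increase visit and shows shifts by visit, while the controlled period does not tabulate that visit and describes its shift table by Week 16.

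**The case against.** The strongest reply is that this is a disclosed convention in an exploratory phase 2 study whose dose recommendation rests on the totality of data. Week 6 results stay in the by-patient listings (SAP 2.3). Clinically significant laboratory changes become adverse events (Protocol 11.6). The safety committee meets about quarterly and sees unblinded data. All of this stands and limits the severity. It does not replace a by-arm table: listings compare nothing, adverse events depend on the investigator's judgment, and committee review protects patients during the trial without altering the reported summaries. The maxima in the by-visit tables are taken after the Week 6 value has been set aside.

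Several stronger readings are tempting and are not supported.

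- A reader might infer that the rise disappears from the tables. A four-week peak can show at Week 8. Protocol 5.1.3 adds that rises above three times the upper limit sometimes took longer to resolve, so the larger ones may still be visible then.
- A reader might put a percentage on how much of a two- or three-week peak Week 8 would miss. That needs an assumed shape of rise and fall. Section 5.1.3 speaks of falling below the upper limit, not of returning to baseline, so such figures go beyond the text.
- A reader might state how far off schedule Week 4 or Week 8 must be before Week 6 is used. The SAP says scheduled visits count whatever the study day only for the 6-minute walk, so the off-schedule behavior for laboratory data is not settled.
- A reader might cite the two-week sample required after escalation in Cohorts 1 and 2 in Part 2 as a further inconsistency. That is a collection rule. The sample comes from an unscheduled visit and gets no analysis window of its own, so it is treated no better than Week 6.
- The Part 1 shift wording could mean through Week 16. Week 16 only is more likely, because Part 2 says each nominal visit, but it is not certain.

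Redacted SAP text and the mock tables cannot be judged; they may treat BNP, for example, separately.

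**Conclusion.** The point holds as a modest reporting improvement. Under the SAP's stated rules, on-schedule Week 6 safety values in Cohorts 3 and 4 never enter the Part 1 by-visit summaries, and this follows from the windows without any assumption about biology. That a two-week transaminase peak can be missed or understated rests on the timing in Protocol 5.1.3 and on a dose increase on Day 28. That the shift tables come too late rests also on reading them as Week 16 only, the likelier reading. How many patients would be affected cannot be estimated from the documents. No claim is made that a safety signal would go undetected during the trial.

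**What to change.** - For Cohorts 3 and 4, and only for safety assessments the protocol schedules at Week 6 (chemistry including eGFR, BNP and NT-Pro BNP, hematology, urinalysis, vital signs, clinic weight), add a Week 6 analysis visit and list it in SAP 3.4.5. One workable choice is Days 36–49, with Week 4 ending on Day 35 and Week 8 starting on Day 50. The protocol ranges 25–31, 39–45 and 53–59 then each fall inside their own window. This also stops a post-increase value being labelled Week 4.
- Leave Table 2 unchanged for the 6-minute walk, pulmonary function tests and anything else not scheduled at Week 6. The primary model is then untouched ("Visits at Weeks 4, 8, 12, and 16 will be used"), and a stray walk or lung function test on Days 36–49 is not moved to a visit where none is planned.
- Provide Part 1 laboratory shift tables at each nominal visit, or on the worst post-baseline value including unscheduled and end-of-treatment results, or both. Keep the Week 16 table.

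The cost is an SAP edit, a few extra tables and separate window sets; no new data are needed. The Week 6 column would be empty for Cohorts 1 and 2 and for anyone enrolled under a protocol version without that visit. Windows would also differ by cohort within the pooled PAH tables, so Week 6 is best shown for Cohorts 3 and 4 separately.
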